This study aims to obtain a diet therapy that can simulate the effect of EEN treatment but has a higher degree of compliance after scientific evaluation of the dietary therapy program CD-C-FOOD, so as to provide more effective approaches for CD treatment and improve the quality of life of patients to a large extent.

Key scientific problems to be solved:

1. To reveal the influence of CD-C-food on the inflammatory response and clinical treatment effect of patients with CD through intestinal microorganisms and metabolites, as well as its internal mechanism, which can be studied by 16S rRNA sequencing mass spectrometry for metabolite detection and pathological observation of animal models

2. To evaluate whether the therapeutic effect of CD-C-food on CD can achieve clinical remission effect. In the clinical pilot trial and subsequent large-sample verification of patients with CD, the study was conducted through observation of clinical inflammatory markers and comprehensive evaluation of clinical effect.

3. To reveal the effective mechanism of CD-C-FOOD and EEN, to conduct in-depth analysis of the process test products of the experimental group, and to conduct specific studies by using 16S rRNA sequencing mass spectrometry and pathological observation of animal models.

4. To evaluate whether the therapeutic effect of CD-C-food on CD can achieve clinical remission effect. In the clinical pilot trial and subsequent large-sample verification of patients with CD, the study was conducted through observation of clinical inflammatory markers and comprehensive evaluation of clinical effect.

3. Research protocol

1. Randomized controlled trials of healthy adults

(1) Specimen collection

A. Inclusion criteria:

- a. 30 healthy adults over the age of 18;
- b. Excluded subjects with any acute or chronic medical conditions (i.e., conditions requiring regular medical attention);
- c. In the past month weight stable (plus or minus 2 kg);
- d. There is no history of intestinal surgery;

e. No antibiotics or steroids have been used in the past 3 months.

B. Research procedure:

- a. The participants were randomly divided into two groups, group 1 and group 2 with 15 people in each group. During the experiment, dietary diary was recorded;
- b. During the first week, participants followed their usual eating habits;

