Adult (36-40 weeks of age) 12 Piebald Virol Glaxo (PVG) heterozygous HLA-B27 and 8 HLA-B7 transgenic rats were studied. B27 rats express the human major histocompatibility complex class I HLA-B27 gene and the related human β 2-microglobulin gene and develop inflammation in their gastrointestinal tract (including ileum). They do not cause intestinal inflammation in a sterile environment, and antibiotic treatment can reduce the severity of ileitis. This model has been widely used in the study of inflammatory bowel disease, including with EEN intervention. The intestinal microbiota of B27 showed a similar phenotype to that of Cd, including an increase in proteobacteria and a decrease in sclerocytes. B7 rats did not have intestinal inflammation and were used as a control. Rats were placed in separate cages and raised under specific non-pathogenic conditions. Weight is monitored.

(2) procedures:

B27 rats was divided into three groups, which were CD-C-FOOD group, EEN group and conventional diet control group. B7 was divided into two groups, EEN group and normal diet control group. The net effect of EEN on their gut microbiota was studied in the B7 group setting without inflammation. There were 2 male rats and 2 female rats in each group, and there was no difference in body weight between groups.

4. Data analysis

The general linear model, Box-Cox transform and Fisher pair test were used for comparison between groups. The bacterial community diversity index among each group can be analyzed by alpha-diversity index. Community richness index (Chao and Ace) and Community diversity index (Shannon and Simpson) were calculated. The similarity and difference of microorganisms in different groups can be analyzed by Unifrac based PCoA. The differences between the groups were analyzed using NMDS (Nonmetric Multidimensional Scaling). PCA(Principal Component Analysis) principal component analysis can be used for grouping analysis between groups. Dietary pathology scores and metabolite markers were analyzed using SPSS, and fecal metabolites were analyzed using PCA, Unifrac based PCOA analysis, and permutation multivariate analysis of variance (PERMANOVA). Pearson test was used for correlation analysis. However, in metabolomic analysis, Spearman rank correlation test was used to compensate for the unbalanced influence of outliers, and Benjamin-Hochberg correction method was used to perform multiple

tests.

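### No test is named for 16S community composition: the plan gives group differences to ordination plots and writes PERMANOVA for fecal metabolites only

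*Combined protocol and SAP*

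**What the plan says.** All the statistical text is in section 3, Research protocol, item 4, Data analysis. It serves three parts: the healthy-adult crossover, the patient trial and the rat experiment.

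- General comparisons: "The general linear model, Box-Cox transform and Fisher pair test were used for comparison between groups". No endpoint is named.
- Alpha diversity: "Community richness index (Chao and Ace) and Community diversity index (Shannon and Simpson) were calculated". No test is named in that sentence.
- 16S composition: "The similarity and difference of microorganisms in different groups can be analyzed by Unifrac based PCoA", then "The differences between the groups were analyzed using NMDS (Nonmetric Multidimensional Scaling"), and for PCA, "principal component analysis can be used for grouping analysis between groups".
- Metabolites: "fecal metabolites were analyzed using PCA, Unifrac based PCOA analysis, and permutation multivariate analysis of variance (PERMANOVA").
- Multiplicity: a correction is named only in the sentence that begins "in metabolomic analysis, Spearman rank correlation test was used to compensate for the unbalanced influence of outliers, and Benjamin-Hochberg correction method".

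Under the key scientific problems (section 2), the first mechanism item asks how the diet acts "through intestinal microorganisms and metabolites, as well as its internal mechanism", with 16S sequencing among the named tools. The third asks about the mechanism of CD-C-food and EEN together. The close of the Background expects the two to influence intestinal microorganisms similarly.

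**The concern.** NMDS, PCoA and PCA turn a distance or data matrix into coordinates, with a stress value or a share of variance explained. None of them tests whether diet shifts the community. If the plots are the evidence, errors can go both ways. Differences between people usually dominate the first axes, so a real diet shift can be hidden inside overlapping clouds and called similarity. Equally, a chance separation of clouds can be called an effect. The first error matters more here, because similarity to EEN is the result the investigators expect, and an overlapping plot would appear to confirm it.

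**Working it through.** **Step 1. Match each data type with its named method.**

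| Data | Named method | Inference for a group contrast |
|---|---|---|
| 16S composition | UniFrac PCoA, NMDS, PCA | none |
| Richness and diversity indices | calculated; the general model sentence may apply | possible, not stated |
| Single taxa, qPCR counts | the general model sentence may apply | possible, not stated |
| Fecal metabolites | PCA, UniFrac PCoA, PERMANOVA | PERMANOVA |

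The gap is in the first row. The last row has its own problem. UniFrac is computed on a phylogenetic tree, and metabolites have none, so the sentence cannot be carried out as written. It may have merged the 16S and metabolite methods, but the text does not settle this.

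**Step 2. Illustrate what a plot can miss.** The documents give no variances, effect sizes or alpha, so every input here except the 30 people is assumed: 30 people on both diets, 60 independent log-scale taxa, between-person SD 1, within-person SD 0.5, 10 taxa shifted by the same amount, a 0.05 level, 200 runs and 199 permutations. PCA stands in for a two-axis ordination.

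- The first two axes hold 16% of the variance.
- The silhouette of the two diets on those axes is -0.025 with no shift and -0.024 with a shift of 0.35, so the plot does not distinguish the two cases.
- PERMANOVA with labels swapped within person rejected in 3%, 88% and 99.5% of runs at shifts of 0, 0.25 and 0.35. Repeat runs with other seeds gave 3% to 5.5%, 85.5% to 88.5%, and 99.5% to 100%.
- PERMANOVA with free permutation rejected in 0% at each of these shifts.

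**Step 3. Why free permutation fails.** With 30 samples per diet, the between-diet sum of squares is (30/2) × (squared length of the mean difference) = 15 × |d|². Its approximate expected values are:

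- Observed, no shift (the person effect cancels): 15 × 60 × 2 × 0.25/30 = 15.
- Observed, shift 0.25: 15 + 15 × 10 × 0.0625 = 24.4.
- Observed, shift 0.35: 15 + 15 × 10 × 0.1225 = 33.4.
- Freely permuted labels (the person effect no longer cancels): 15 × 60 × 2 × (1 + 0.25)/30 = 75.

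The observed values lie far below the free-permutation reference, so that version of the test cannot reject. Within-person swaps keep the reference near 15. A second set of assumptions (20 features, SDs 2 and 1, shift 0.25 in every feature) gave the same picture: 0% for free permutation and 73.5% for within-person permutation.

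**Step 4. Feasibility in the rats.** Groups have four animals: 3 × 4 = 12 B27 and 2 × 4 = 8 B7, as the plan states.

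- One pair, 4 v 4: C(8,4)/2 = 70/2 = 35 distinct partitions, so the smallest p is 1/35 = 0.029. With Bonferroni over the three B27 pairs it is 3/35 = 0.086.
- Three-group B27 omnibus: 12!/(4!³ × 3!) = 5,775 partitions, so the smallest p is 1/5,775 = 0.00017.

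In the 30-person crossover the floor is 2/2³⁰, which is no practical limit.

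**The case against.** A reader might infer that the microbiome data get no test at all and are compared only by eye. The documents do not support that. The opening sentence on the general linear model, Box-Cox and the Fisher test is general and comes just before the diversity indices, so it may well cover richness, diversity, single taxa and qPCR counts. This could carry weight: under the Step 2 assumptions, paired per-taxon tests with Benjamini-Hochberg found at least one taxon in 55.5% of runs at a shift of 0.25 and 91.5% at 0.35 (3.5% under the null). Still, the sentence names no endpoint, and two quite different communities can share a Shannon value, so the gap for composition remains.

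A reader might also infer that the whole mechanism question goes untested. It does not, because the metabolite half is given PERMANOVA. If the metabolite sentence is a garbled merger, PERMANOVA may have been meant for 16S as well. That is a reason to rewrite the sentence rather than to rely on it.

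The simulation can fairly be faulted for changing two things at once: it sets an unpaired plot against a paired test. That criticism stands. Much of the gain comes from respecting the pairing, and adding PERMANOVA with free permutation would have detected nothing in these runs.

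Two further objections stand and shape the fix. Within-participant label swaps do not suit parallel rat groups, nor a patient procedure that describes CD-C-Food only. And PERMANOVA tests difference, so a large p-value would not show that the two diets act alike.

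**Conclusion.** The concern holds in limited form. No test of 16S community composition is specified, and the only multivariate test is written for metabolites, with a distance that does not suit them. This rests on the text alone. The simulated rejection rates are illustrative: they depend on assumed SDs, shifts and independent taxa, and on PCA standing in for NMDS and UniFrac. The permutation floors in the rats follow from the stated group sizes.

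Calling this a must-fix would be too strong. The analysis is mechanistic, clinical remission is a separate key problem that this leaves untouched, and the omission can be repaired before analysis. It is a should-fix: a method that tests nothing is named where a test on distances already required for the PCoA is available.

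**What to change.** Rewrite the composition and metabolite sentences of the Data analysis section to say the following.

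- NMDS, PCoA and PCA are for display only.
- 16S composition is tested by PERMANOVA on weighted and unweighted UniFrac distances, reporting R² and p. A dispersion test (PERMDISP) is reported beside it, because one fixed formula and a personalised menu may differ in spread.
- Healthy crossover: diet labels are permuted within participant. Name the samples compared (ends of weeks 2 and 5) and say how period and the pre-diet samples (ends of weeks 1 and 4) are handled.
- Patients: as no comparison diet is described, change over time is tested with permutation restricted within patient.
- Rats: free permutation, with the three-group B27 omnibus test first and pairs afterwards.
- Metabolites: a distance that needs no phylogeny is named, and the text states which data PERMANOVA covers.
- The general model sentence lists its endpoints, including alpha diversity and taxa if intended, with a multiplicity rule for the 16S tests.
- A non-significant PERMANOVA will not be read as evidence that CD-C-Food and EEN have similar effects on the microbiome.

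The cost is a short paragraph rather than a single sentence, because the three parts need different permutation schemes, plus a few lines of code. No new samples or measurements are needed.
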